6.0 Data Analysis

Describe plans for data analysis, including stratification by sex, gender and diversity. Indicate whether data will be analysed by the investigators themselves or by other professionals. Specify what statistical software packages will be used and if the study is blinded, when the code will be opened. For clinical trials, indicate if interim data analysis will be required to determine further course of the study.

Data analysis must comply with ICH E9 Guideline and ICH E9(R1) Guideline. All relevant data collected in the trial should be considered in the statistical considerations section.

The analysis will be conducted on all participant data at the time the trial ends.

Statistics for primary end-point data and parametric secondary end-point data will be presented via means (alternatively, LSMEANS) with standard deviations; primarily two-tailed Student's t-test will be used for analysis with significance level of $p \leq 0.05$. For non-parametric analysis, such as lifetime data, Kaplan-Meier analysis will be used with significance level of $p \leq 0.05$. Some data might be expressed and analyzed as % values, such as the occurrence of unscheduled IV rehydration.

Analysis of secondary endpoints will be performed through the same method of the primary endpoint, which is found via a one- sided two sample unequal variance Student's t-test. The scale for each secondary endpoint will be nominal and will be determined at a single endpoint, which is at the end of intervention. The results will be presented by LSMEANS (Least-squares Means) with standard errors.

Primary Endpoint:

Reduction in stool output volume (ml/hour) over a treatment period measured and plotted as total stool output during 12-hour stool collection at every 12 hours for 72 hours.

Secondary Endpoints:

- Time until the stool volume output of 200mL/hour or less. Duration of stool output in excess of 200mL/hour per patient will be recorded between the start and end of the treatment for both treatment groups.
- Time until recovery. Duration of diarrhea until the passage of first non-watery stool or no stool for 12 hours or the end of treatment (72 hours) will be derived from date and time records in daily stool charts.
Number of unscheduled IV rehydration episodes per treatment. The number of unscheduled IV rehydration episodes per treatment will be recorded for the entire duration of the treatment. Unscheduled IV rehydration is defined as "receipt of IV fluid during the maintenance phase of hydration due to development of severe dehydration or some dehydration with high purging (>15 ml/kg/hour) or persistent vomiting (>3 episodes/hour), or failure to take ORS for any reason"
- Duration of IV rehydration for the entire treatment period per treatment group and per each 24-hour period of treatment.
- Number of recovered subjects within treatment group. The number of recovered subjects will be recorded as total for the entire treatment duration, and as number of recoveries per each 24-hour period of treatment.
- Safety will be measured by the proportion of patients that will present with AE following administration of VR-AD-1005.

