5.0 Sample Size Calculation and Outcome (Primary and Secondary) Variable(s)

Clearly mention your assumptions. List the power and precision desired. Describe the optimal conditions to attain the sample size. Justify the sample size that is deemed sufficient to achieve the specific aims.

Planned screening is 500 participants. ITT (intention to treat) group is 150 patients. Enrollment will stop once 150 participants are recruited, or once 100% of per-protocol dataset (PP) is achieved. Sample size was calculated based on the mean volume of stool output in cholera patients. Mean stool output was assumed at 280 ± 156 g/kg²²⁻²⁴. Assuming 33% reduction (alternative hypothesis) vs no reduction (null hypothesis), sample size was calculated using GraphPad Prism software for two-tailed t-test with alpha 5% and power 0.8. Using recruitment of 50 participants per arm (100 total), power level of 0.82 can be achieved. Although, this is a sufficient level of power for the projected study, data points lost due to participant drop-out, cross-over to other study arms, withdrawal and missing data will affect the power of the study. We calculated that recruitment of up to 75 patients per study arm would allow power of 0.94.

Endpoints associated with primary and secondary objectives, and justification for endpoints are given below (Table 1).

Table 1-Primary and Secondary Objectives and Endpoints

OBJECTIVES	ENDPOINTS	JUSTIFICATION FOR ENDPOINTS
Primary		

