Secondary Endpoint 1, assessment of hydration control. There are two measurable parameters to be assessed in the patient hydration. Parameter 1 is the number of unscheduled hydration episodes. The numbers will be derived from the individual rehydration records, and the number of patients receiving IV rehydration will be expressed in % and compared for control and study intervention group. Alternatively, total number of IV rehydration episodes can be expressed as means for control and study intervention group and analyzed using Student's t-test. Parameter 2 is the volume of the oral rehydration solution received during the course of interventional treatment. Total volume of rehydration solution (oral and IV where applicable) will be derived from the individual rehydration records, expressed in ml/kg of patient weight, and analyzed as means using unpaired Student's t-test. Analysis subgroups will include 1) total hydration received over the course of study after first administration of interventional medication, and 2) hydration received during first 12 hours and 3) hydration received during first 24 hours.

Secondary Endpoint 2. Assessment of duration of diarrhea. Total duration of diarrheal illness is an important parameter in the assessment of antidiarrheal treatment efficacy. Study intervention is expected to reduce the overall duration of the diarrhea. Duration of diarrhea is assessed from first administration of study intervention until the termination of diarrhea, which is defined as first formed stool, or no stool for 12 consecutive hours. Duration of diarrhea will be derived from individual stool charts. Kaplan-Meier survival curves will be built to compare duration of diarrhea between control and intervention groups.

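### Section 6.0 describes the primary test as two-tailed at 0.05 and then as one-sided with no level of its own, so the rule for declaring benefit is not fixed

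*Combined protocol and SAP*

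**What the plan says.** Section 5.0 sizes the trial on a two-tailed test: "sample size was calculated using GraphPad Prism software for two-tailed t-test with alpha 5% and power 0.8". Its inputs are there too: "Mean stool output was assumed at 280 ± 156 g/kg", with a 33% reduction under the alternative. It puts power at 0.82 with 50 per arm and 0.94 with 75 per arm.

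Section 6.0 then describes the primary test twice, in consecutive paragraphs.

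- The first covers the primary endpoint and the parametric secondary endpoints: "primarily two-tailed Student's t-test will be used for analysis with significance level" of p ≤ 0.05. It keeps Kaplan-Meier for lifetime data, at the same level, and allows some measures to be handled as percentages.
- The second concerns secondary endpoints and says they are analysed by "the same method of the primary endpoint, which is found via a one- sided two sample unequal variance" t-test. It gives no significance level. It adds: "The scale for each secondary endpoint will be nominal and will be determined at a single endpoint".

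Section 6.2.1, where the primary analysis is set out, names an unpaired Student's t-test. The null is no difference from placebo and the alternative is a reduction. It states neither sidedness nor level.

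Section 6.3 gives methods endpoint by endpoint. Unscheduled IV rehydration is compared as percentages of patients or, alternatively, as mean episode counts. For duration of diarrhoea, "Kaplan-Meier survival curves will be built to compare duration of diarrhea between control and intervention groups". Time above 200 ml/hour is compared by t-test.

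**The concern.** Both paragraphs of section 6.0 claim to describe the primary test, and they differ on sidedness and on the variance assumption. The trial's main conclusion depends on which one is followed. For example, a one-sided p of 0.03 in favour of the drug meets a one-sided 0.05 rule, while the corresponding two-sided p of 0.06 fails the two-tailed rule.

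The second paragraph also cannot be carried out alongside section 6.3. A t-test compares means and has no meaning on a nominal scale. Diarrhoea duration is cut off at 72 hours, so a t-test would treat anyone not recovered by then as having a known duration.

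**Working it through.** **1. Where sidedness and level are stated**

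| Place | Test | Sidedness | Level |
|---|---|---|---|
| 5.0 | t-test | two-tailed | 5% |
| 6.0, first paragraph on tests | Student's t | two-tailed (primarily) | 0.05 |
| 6.0, next paragraph | unequal-variance t | one-sided | none given |
| 6.2.1 | unpaired Student's t | none given | none given |

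Section 6.2.1 cannot break the tie. Its no-difference null fits a two-sided test, and its directional alternative could be cited for a one-sided one.

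**2. Reproducing the stated power**

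Inputs from section 5.0: control mean 280 g/kg, SD 156 g/kg in both arms, 33% reduction, 1:1 allocation.

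- Difference: 0.33 × 280 = 92.4 g/kg, or 92.4 / 156 = 0.592 SD.
- Noncentrality: 92.4 / (156 × √(2/n)), which is 2.96 at n = 50 and 3.63 at n = 75.
- Power comes from the noncentral t with 2n − 2 degrees of freedom.

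| Per arm | Stated | Two-sided 0.05 | One-sided 0.05 | One-sided 0.025 |
|---|---|---|---|---|
| 50 | 0.82 | 0.835 | 0.903 | 0.835 |
| 75 | 0.94 | 0.950 | 0.975 | 0.950 |

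The stated figures are within 0.015 and 0.010 of the two-sided values. They are 0.083 and 0.035 away from the one-sided 0.05 values. The match to the two-sided test is close but not exact. A one-sided test at 0.025 has the same power as the two-sided test at 0.05, so these figures rule out only the one-sided 0.05 reading.

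**3. Chance of a false claim of benefit under the null**

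- Two-sided 0.05: 0.05 / 2 = 0.025 in the direction of benefit.
- One-sided 0.05: 0.05 in that direction, a ratio of 2.
- One-sided 0.025: 0.025, so no increase.

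A simulation with 75 per arm and normal data (200,000 trials) gave 0.0246 for the two-sided test in the direction of benefit and 0.0494 for the one-sided unequal-variance test at 0.05.

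**4. Smallest observed reduction that would be significant at 75 per arm**

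Standard error: 156 × √(2/75) = 25.5 g/kg. Critical t on 148 degrees of freedom: 1.976 two-sided and 1.655 one-sided, both at 0.05.

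- Two-sided: 1.976 × 25.5 ≈ 50.3 g/kg, or 50.3 / 280 = 18% of the control mean.
- One-sided: 1.655 × 25.5 ≈ 42.2 g/kg, or 42.2 / 280 = 15%.

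An observed reduction between these two values is positive under one paragraph and negative under the other.

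**5. The nominal-scale sentence against the endpoint list**

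The secondary efficacy endpoints in section 6.0 are times, durations, an episode count and a number recovered. A patient's recovery status is nominal, but the times, durations and count are not. Section 6.3 uses Kaplan-Meier curves for diarrhoea duration, states that this endpoint is analysed non-parametrically, and offers percentages for unscheduled IV rehydration. A single t-test for all secondary endpoints contradicts the first two, and the percentage option as well.

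**The case against.** The strongest reply is that the intended rule can be identified. The sentence that assigns a test to the primary endpoint is two-tailed, and so is the sample size. The one-sided wording is a subordinate clause in a paragraph about something else, and is probably a drafting remnant. This is likely right about intent, but it does not remove the conflict. The clause is current text, it names the primary endpoint, and the word primarily weakens the two-tailed commitment.

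Several stronger readings are tempting, and the documents do not support them.

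- A reader might infer that the plan doubles the false-positive rate. The one-sided sentence gives no level, so the doubling depends on reading 0.05 across from the preceding paragraph. It concerns the direction of benefit only; the total type I error is 5% for either test run at 0.05.
- A reader might infer that the analyst could pick the direction after seeing the data. Section 6.2.1 fixes the direction as a reduction. What stays open is the threshold, which matters when the one-sided p lies between 0.025 and 0.05.
- A reader might infer that harm goes untested. That holds only for increased stool output under the one-sided reading. The two-tailed rule covers both directions, and section 6.4 compares adverse event percentages separately.
- A reader might infer that the secondary endpoints have no usable method. Section 6.3 supplies methods for the endpoints it covers, so the nominal-scale sentence is a wording conflict and the lesser part of this point.

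The difference in variance assumption has little effect with equal arms, but one version should still be named.

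**Conclusion.** The contradiction stands, and nothing else in the document settles it. As written, the primary success rule has two readings.

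The sizes above assume that the one-sided test would be run at 0.05, that the SD is 156 g/kg in both arms, that there are 75 patients per arm, and that outcomes are normal, as section 6.2.1 assumes. If a one-sided 0.025 test was meant, the error in the direction of benefit does not rise, but the plan still fails to state its level. Section 5.0 supports settling on two-sided 0.05. The matter should be resolved before unblinding, because it can change the trial's primary conclusion.

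**What to change.** 1. In section 6.0, delete the whole paragraph on secondary endpoints that contains the one-sided clause, including its nominal-scale sentence.
2. State once in section 6.0, and repeat in section 6.2.1, that the primary test is one named two-sample t-test with one stated variance assumption, two-sided at 0.05, to match section 5.0. Drop the word primarily.
3. Let the endpoint-specific methods in section 6.3 govern the secondary endpoints, also two-sided at 0.05, and name a log-rank test to accompany the Kaplan-Meier curves.

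The number recovered and the duration of IV rehydration have no entry of their own in section 6.3. After the deletion they fall under the first paragraph on tests in section 6.0, so it is worth confirming that this is intended.

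The cost is a wording amendment to the combined protocol and SAP, handled under section 8.2. It should be in place before the randomisation tables go to the biostatisticians (section 4.4.6.1). Sample size and data collection do not change. Two-sided 0.05 keeps power at about 0.835 with 50 per arm and 0.950 with 75 per arm.

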6.2. Analysis Supporting Primary Objectives

6.2.1. Statistical Model, Hypothesis, and Method of Analysis

Primary Endpoint:

Reduction in stool output volume over a treatment period.

Primary Endpoint 1., Hypothesis 1. Treatment with VR-AD-1005 reduces stool output in patients with diarrhea due to *V. cholerae* infection. Null hypothesis is stated as no statistically significant difference in stool output volume as compared to placebo; alternative Hypothesis 1 is stated as statistically significant reduction in stool output volume in patients treated with VR-AD- 1005.

Two analytical approaches are proposed. Approach 1 will be based on the total quantity of stool purged by participant during the intervention administration period. Stool output will be expressed as g/kg body weight based on the stool charts, and the means will be compared between intervention and placebo groups using Student's unpaired t-test. In approach 2, stool purging is measured and plotted as total stool output in ml/kg/12 hours based on the individual stool collection charts. Weight of stool will be converted to volume using 1:1 weight/volume ratio. Diarrhea of cholera resolves rapidly, and majority of patients are expected to recover within 30-50 hours after randomization. 12-hour analysis increments allow a better insight into the onset and timing of the effect of study intervention as compared to cumulative data over the duration of the treatment. Means will be compared for each 12-hour period after first intervention administration using unpaired Student's t-test. Normal distribution is assumed for both cases. Analysis will be conducted in the ITT, MITT and PP groups. Missing data and outliers will be handled using imputation technique. Non-adherence and lost to follow-up patients will be categorized into the appropriate group and handled accordingly. No subtractions will be made from the ITT group after randomization assignment.

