6.3. Analysis Supporting Secondary Objectives

Analysis of secondary end-points is not dependent on the analysis of the primary end-point.

Secondary Endpoint 1, Hypothesis 2. Treatment with VR-AD-1005 improves hydration control in patients with diarrhea due to *V. cholerae* infection. Null hypothesis is stated as no statistically

significant difference in the number of unscheduled hydration episodes as compared to placebo; alternative hypothesis 2 is stated as statistically significant improvement in hydration control, expressed as number of unscheduled rehydration episodes over the treatment period; in patients treated with VR-AD-1005. Unscheduled IV rehydration is defined as “receipt of IV fluid during the maintenance phase of hydration due to development of severe dehydration or some dehydration with high purging (>15 ml/kg/hour) or persistent vomiting (>3 episodes/hour), or failure to take ORS for any reason”

Secondary Endpoint 2, Hypothesis 3. Treatment with VR-AD-1005 shortens duration of diarrhea in patients with diarrhea due to *V. cholerae* infection. Null hypothesis is stated as no statistically significant difference in the duration of diarrhea as compared to placebo; alternative hypothesis 2 is stated as statistically significant reduction in the duration of diarrhea, expressed as number of days till normalization of stool, in patients treated with VR-AD-1005.

Secondary Endpoint 3, Hypothesis 4. Treatment with VR-AD-1005 shortens duration of stool output in excess of 200ml/hour in patients with diarrhea due to *V. cholerae* infection. Null hypothesis is stated as no statistically significant difference in the duration of stool output >200 ml/hour as compared to placebo; alternative hypothesis 2 is stated as statistically significant reduction in the duration of diarrheal output >200 ml/hour, expressed in hours, in patients treated with VR-AD-1005.

Analysis:

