Secondary Endpoint 3. Duration of stool output in excess of 200ml/hour. As stated above, duration of diarrheal disease in cholera is limited, averaging 30-35 hours²⁴. This could mask the beneficial effect of antidiarrheal treatment (as measured solely by stool quantification) if high initial stool output terminates abruptly. In order to establish the time course of the study intervention's effect, in addition to analyzing the total duration of diarrhea in patients we need to introduce a parameter that combines the measured quantity of stool output and the time factor, addressing the question whether interventional medication can reduce the severity of diarrhea in the early stage of administration of study intervention. For analysis, individual stool charts will be used to calculate stool output per patient per 12-hour period and express it as stool volume in ml/hour. Duration of time when stool

output is in excess of 200ml/hour will be calculated for each participant, expressed as means for control and study intervention group and analyzed using Student's t-test.

Normal distribution is assumed for Endpoints 1 and 3. Non-parametric statistics is used in the analysis of Endpoint 2. Analysis will be conducted in the ITT, MITT and PP groups. Missing data and outliers will be handled using imputation technique. Non-adherence and lost to follow-up patients will be categorized into the appropriate group and handled accordingly. No subtractions will be made from the ITT group after randomization assignment.

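### Section 6.0 calls each secondary endpoint nominal and read once at the end of intervention, which contradicts the listed endpoints and their methods and leaves the number recovered without a workable comparison

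*Combined protocol and SAP*

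**What the plan says.** Section 6.0 states that secondary endpoints follow the method of the primary endpoint, which it describes there as a "one- sided two sample unequal variance Student's t-test". It adds: "The scale for each secondary endpoint will be nominal and will be determined at a single endpoint, which is at the end of intervention". Results are to be shown as least-squares means with standard errors.

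The preceding paragraph of 6.0 names a two-tailed Student's t-test as the main method. It also says "For non-parametric analysis, such as lifetime data, Kaplan-Meier analysis will be used with significance level of" p ≤ 0.05. Section 5.0 sizes the trial for a "two-tailed t-test with alpha 5% and power 0.8".

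The secondary endpoints in 6.0 and Table 1 are time until output falls to 200 ml/hour, time until recovery, number of unscheduled IV rehydration episodes, duration of IV rehydration, number recovered, and the proportion with adverse events. On the number recovered, 6.0 says "The number of recovered subjects will be recorded as total for the entire treatment duration", and the same sentence goes on to require the count for each 24-hour period as well. Table 1 agrees.

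Section 6.3 uses Kaplan-Meier curves for duration of diarrhoea and t-tests on means for time above 200 ml/hour and for rehydration volume. It gives percentages or mean counts for rehydration episodes.

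On timing, treatment lasts 72 hours (Table 1). Section 6.2.1 says the "majority of patients are expected to recover within 30-50 hours after randomization", and Section 6.3 says "duration of diarrheal disease in cholera is limited, averaging 30-35 hours".

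**The concern.** Read literally, one sentence in 6.0 turns times, durations and counts into categories read at a single moment, and then applies a t-test and least-squares means to them. A nominal variable has no mean to test. The plan does not say which rule prevails where 6.0 disagrees with itself or with 6.3.

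For most endpoints 6.3 supplies a usable alternative. For the number recovered it does not: 6.3 states no hypothesis or test for it, and the list of comparisons in 6.1 omits it. The sentence in 6.0 is the only text that sets an analysis time for that endpoint, and it points to the end-of-treatment total. That is where the two arms are likely to look most alike. A real shortening of illness could then be reported as no difference in the number recovered, beside a favourable Kaplan-Meier result in the same patients. The choice between the conflicting rules would be left until after the data are seen.

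**Working it through.** **1. The plan's own power figure.** The only power in the documents is for total stool output (Section 5.0): mean 280, SD 156 g/kg, 33% reduction, 5% two-tailed. The difference is 0.33 × 280 = 92.4, so d = 92.4/156 = 0.592. The noncentral t gives 0.835 at 50 per arm (stated 0.82) and 0.950 at 75 per arm (stated 0.94), so the stated figures reproduce within 2 points. A one-sided test would give 0.903 and 0.975, which do not match. The trial was therefore sized two-sided, and the one-sided sentence does not describe the primary method. No power is given for any recovery endpoint.

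**2. Scale and timing, endpoint by endpoint.**
- Times to 200 ml/hour and to recovery, and duration of IV rehydration: not nominal. The two times are not single end readings.
- Unscheduled IV episodes: a count.
- Number recovered and proportion with adverse events: yes/no per patient, so a nominal scale fits, but a t-test with least-squares means is not the natural analysis.
- Recoveries per 24-hour period: several readings, not one.

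**3. What a single 72 h reading can show.** Inputs from the documents: 75 per arm, 72 h of treatment, mean illness 30-35 h. Assumed, not in the documents: Weibull recovery times with shape 1 to 3, the 30-35 h mean taken as the control mean, and treatment shortening the mean by 33% (borrowed from the stool-output assumption) or 20%. All 75 per arm are taken as evaluable.

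Proportion recovered by time t: F(t) = 1 − exp(−(t/s)^k), with s = mean/Γ(1 + 1/k).
Power = Φ[(|p1 − p2| − 1.96·se0)/se1], where se0 uses the pooled and se1 the separate variances.

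Example with mean 32.5 h, k = 2 and 33% shorter: s = 36.67 and 24.57. At 72 h, p = 0.9788 and 0.9998, se0 = 0.0168 and se1 = 0.0167. Power = Φ[(0.0210 − 0.0329)/0.0167] = Φ(−0.71) = 0.24. Replacing 1.96 by 1.645 (one-sided) gives Φ(−0.40), about 0.35.

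Control mean 32.5 h, 33% shorter (control/treated % recovered, then power; log-rank simulated with 1,500 runs, censored at 72 h):

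| Shape | 24 h | 48 h | 72 h | 72 h, Fisher | Log-rank |
|---|---|---|---|---|---|
| 1 | 52/67: 0.44 | 77/89: 0.49 | 89/96: 0.40 | 0.281 | 0.63 |
| 1.5 | 42/63: 0.73 | 79/94: 0.79 | 94/99: 0.45 | 0.205 | 0.95 |
| 2 | 35/61: 0.91 | 82/98: 0.90 | 98/100: 0.24 | 0.005 | 0.99 |
| 3 | 25/61: 1.00 | 90/100: 0.81 | 100/100: 0.04 | 0.00 | 1.00 |

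Over means of 30, 32.5 and 35 h and all four shapes, control recovery at 72 h runs from 87% to almost 100%. Power ranges:
- 33% shorter: 72 h 0.03-0.54; 24 h 0.43-1.00; 48 h 0.48-0.95; log-rank 0.61-1.00.
- 20% shorter: 72 h 0.03-0.27; 24 h 0.16-0.72; 48 h 0.19-0.80; log-rank 0.25-0.98.

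Log-rank and the 48 h count beat the 72 h reading in every scenario. The 24 h count does so in all but three of the 20% cases, where it falls short by at most 0.02.

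**4. Ceiling without a distribution.** If every treated patient recovered, power at 75 per arm (normal approximation / Fisher) would be 0.81 / 0.77 with 90% control recovery, 0.50 / 0.17 with 95%, and 0.23 / 0.004 with 98%.

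**5. Unit of duration.** Hypothesis 3 in 6.3 has duration "expressed as number of days till normalization of stool". A third off 30-35 h is 0.33 × 30 = 9.9 h to 0.33 × 35 = 11.6 h, under half a day.

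**The case against.** The best defence is that the sentence is a stray remark that no analyst would follow. The same section gives Kaplan-Meier to lifetime data, 6.3 has working methods for the main secondary endpoints, and recoveries per 24-hour period are part of the stated endpoint with the same standing as the total. The number recovered may be meant only as a description. A 72 h proportion and a time-to-event curve answer different questions, so differing results would not strictly be a contradiction. "End of intervention" may also not mean 72 h, since Section 4.0 lets treatment end earlier on recovery.

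Much of this stands. A reader might infer that 6.0 fixes every secondary endpoint as a single end reading, or that the trial cannot show a difference in recovery. The documents support neither: the sentence contradicts the other provisions and does not override them, and time until recovery keeps its Kaplan-Meier analysis. A reader might also infer that nearly everyone will have recovered by 72 h. The documents say only that a majority recover within 30-50 hours, and they give no share at 72 h.

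The earlier-stopping point does not help the total. Patients who stop on recovery count as recovered and the rest are read at 72 h, so, withdrawals aside, the total is still the share recovered by 72 h. Nor does the defence supply a test or a chosen time point for the number recovered.

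**Conclusion.** The point holds as an internal contradiction that should be resolved before unblinding. The rule in 6.0 does not fit most of the endpoints it governs, is paired with a test unsuited to a nominal scale, and differs in sidedness from the paragraph before it and from the sample size section. Its practical cost falls on the number recovered: on the end-of-treatment total, power for a 33% shortening is about 0.03-0.54, lower than the log-rank and 48 h comparisons throughout and lower than the 24 h comparison in every 33% scenario.

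These figures rest on assumed Weibull shapes, an assumed effect on duration and full evaluability, so the ranges matter more than any single value. The normal approximation is unreliable near 100%, and Fisher's test gives less power at 72 h. Losses would lower every figure. The calculations do not make 48 h the one right time point: 24 h does better for some distributions and 48 h for others. The use of days in Hypothesis 3 is a minor wording matter, since nothing says durations will be rounded to whole days.

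**What to change.** - In 6.0, delete the sentence on a nominal scale and a single reading, and reconcile the one-sided unequal-variance t-test sentence before it with the two-tailed test stated earlier in the section.
- Name the scale, time point and test for each secondary endpoint. Include duration of IV rehydration, for which 6.3 also gives no method.
- In 6.3, specify a log-rank test with the planned Kaplan-Meier curves as the main between-arm comparison of recovery.
- For the number recovered, compare the cumulative proportions recovered by 24 h and 48 h after first dose with a two-sided test of proportions, with 72 h as supportive. Build these from the per-24-hour counts already planned, and add the endpoint to the list in 6.1.
- In Hypothesis 3, express duration of diarrhoea in hours, in line with the date and time records that 6.0 already uses.

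The cost is wording in the protocol and SAP. No new data, visits or patients are needed.
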